### Secondary Objectives

- To evaluate the safety of oral AG-221 when administered with SC azacitidine.
- To characterize the PK of oral AG-221 when administered with SC azacitidine.
- To evaluate the effect of oral AG-221 when administered with SC azacitidine versus SC azacitidine alone on health-related quality-of-life (HRQoL) outcomes.

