**Table 2: Study Endpoints (Continued)**

Endpoint	Name	Description	Timeframe
	One-year survival	The probability of survival at 1 year from randomization	Approximately 30 months
	PK parameters	Plasma concentrations and pharmacokinetic parameters of AG-221.	Approximately 30 months
	HRQoL outcomes	European Organization for Research and Treatment of Cancer Quality-of-Life questionnaire (EORTC QLQ-C30) ( Appendix N ) and EuroQoL Group EQ-5D-5L instrument ( Appendix O )	Approximately 30 months

Abbreviations: [REDACTED] AE = adverse event; AML = acute myeloid leukemia; [REDACTED] CR = morphologic complete remission; CRh = morphologic complete remission with partial hematologic recovery; CRi = morphologic complete remission with incomplete neutrophil recovery; CRp = morphologic complete remission with incomplete platelet recovery; DRT = Dose Review Team; EORTC= European Organization for Research and Treatment of Cancer; HI = hematologic improvement; HI-E = hematologic improvement erythroid response; HI-N = hematologic improvement neutrophil response; HI-P = hematologic improvement platelet response; HRQoL = Health-related Quality-of-Life; IWG = International Working Group; MDS = myelodysplastic syndrome; MLFS = morphologic leukemia-free state; [REDACTED] PK = pharmacokinetics; PR = partial remission; SC = subcutaneous.

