- ee Intensive PK sampling is performed as defined in Table 6 for AG-120 subjects in the Phase 1b Expansion on all subjects, and Table 7 in Phase 2 for AG-221 subjects at select sites for the first 6 - 12 subjects. Sparse PK sampling will be performed on all other AG-221 subjects at the selected sites as well as all other sites as defined in Table 8.

ff Cycle 2 only.

gg Every 4 weeks ( $\pm$  7 days) for survival follow-up until death, lost to follow-up, withdrawal of consent for further data collection or the End of Trial, whichever occurs first.  
Subsequent AML therapies should be collected at the same time schedule. See Section 6.3 for details.

■ [REDACTED]

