**Table 8: AG-221 Sparse Pharmacokinetic Sampling in Phase 2**

	Cycle 2	Cycle 3
	D1	D1
Pre-dose a	X	X
Post-dose		
4.0 hr a	X	-

a Within 30 minutes prior to AG-221

b ± 10 minutes

Note: Sparse pharmacokinetic (PK) sampling for AG-221 will be conducted at all sites during Phase 2. Subjects who participate in the intensive PK will not have additional samples collected.

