## 6.6. Pharmacokinetics

Pharmacokinetic sampling for AG-120 will be conducted on all subjects during Phase 1b AG-120 expansion stage as detailed in Table 6.

During Phase 1b AG-120 expansion stage, subjects enrolled in the AG-120 combination treatment arm will undergo intensive PK assessments, in order to evaluate the PK profile of AG-120 when administered with azacitidine. On Days 1 of Cycle 1 and 2, blood samples will be collected at the following time points: pre-dose (within 30 minutes prior to AG-120) and 0.5 hours ( $\pm$  10 minutes), 2 hours ( $\pm$  10 minutes), 3 hours ( $\pm$  10 minutes), 4 hours ( $\pm$  10 minutes), 6

hours ( $\pm$  10 minutes), and 8 hours ( $\pm$  10 minutes) post-dose. Pre-dose blood samples (trough) will also be obtained on C1D15.

During Phase 2 AG-221 randomization stage, the first twelve subjects at selected sites in the AG-221 combination treatment arm will undergo intensive PK assessments (Table 7) over a 24-hour period on C2D1 to C2D2, in order to evaluate the PK profile of AG-221 when administered with azacitidine. Blood samples will be collected at the following time points: pre-dose (within 30 minutes prior to AG-221) and 2 hours ( $\pm$  10 minutes), 3 hours ( $\pm$  10 minutes), 4 hours ( $\pm$  10 minutes), 6 hours ( $\pm$  10 minutes), 8 hours ( $\pm$  10 minutes,) and 24 hours ( $\pm$  10 minutes) post-dose. Pre-dose blood samples (trough) will also be obtained on C3D1.

The subjects not being assessed for intensive PK in the AG-221 treatment arm during the Phase 2 segments will undergo sparse PK samples for measurement of AG-221 concentration (Table 8). Blood samples will be collected at pre-dose (within 30 minutes prior to dosing) and 4 hours ( $\pm$  10 minutes) post-dose on Day 1 of Cycle 2, and pre-dose on Day 1 of Cycle 3.

No PK samples will be collected from subjects who are randomized to the azacitidine alone treatment arm.

The peripheral blood sample should be collected by an in-dwelling catheter or by venipuncture into sample collection tubes. Sample collection kits and supplies will be provided by the sponsor or sponsor-designated vendor. Blood samples for sparse PK should be processed promptly and plasma harvested and stored according to the instructions in the Study Reference and/or Study Laboratory Manual.

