4.4. Sample Size Determination

The Phase 1b dose-finding stage will enroll a total of approximately 24 subjects. Additional subjects may be enrolled in a dose level to replace subjects who are not evaluable for the primary endpoint, or for further exploring safety, PK, PK/pharmacodynamics, or preliminary clinical activity.

In Phase 1b AG-120 expansion stage, to ensure acceptable toxicity at the RCD, up to 15 subjects will be accrued into the AG-120 expansion phase. Based on a sample size of 18 AML subjects treated at RCD (i.e., 15 subjects in the dose expansion and around 3 subjects in the dose escalation), there is 95% probability of detecting 1 or more AEs with an underlying rate of 15%, and 85% probability of detecting 1 or more AEs with an underlying rate of 10%.

In Phase 2 AG-221 randomized stage, subjects with AML with IDH2 mutation will be randomized to receive oral AG-221 + SC azacitidine versus SC azacitidine in a 2:1 ratio. A minimum of 99 subjects will be randomized in this phase with 66 subjects in the oral AG-221 + SC azacitidine arm, and 33 subjects in the SC azacitidine monotherapy arm. The statistical comparisons will be conducted for oral AG-221 + SC azacitidine versus azacitidine monotherapy. Assuming an ORR of 30% in the azacitidine monotherapy and an ORR of 50% for oral AG-221 + SC azacitidine arm, the sample size of 66 subjects in AG-221 + SC azacitidine arm and 33 patients in SC azacitidine monotherapy arm will provide 75% power to detect a 20% difference in ORR at a two-sided type I error rate of 0.2. The multiple comparisons were not considered in the sample size calculation.

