12.2. Plasma Sample Collection

Blood samples for intensive PK assessments of AG-221 in plasma will be collected at the following time points: predose (0 hour) and 2, 3, 4, 6, 8 and 24 hours post-dose in the first twelve subjects on C2D1 in each of treatment arms in Phase 2.

Blood samples for intensive PK assessments of AG-120 in plasma will be collected at the following time points: pre-dose and 0.5, 2, 3, 4 hours, 6, and 8 hours post-dose on Days 1 of Cycle 1 and 2 in Phase 1b.

Plasma concentrations of AG-221 or AG-120 will be summarized by nominal time points, including mean, standard deviation, % coefficient of variation (CV%), geometric mean, geometric CV%, minimum, median, and maximum. Mean (\pm standard deviation) plot of plasma concentrations will be presented in both linear scale and semi-logarithmic scale. Figure will be provided.

The subjects not being assessed for intensive PK in the AG-221 treatment arm during the Phase 2 segments will undergo sparse PK samples for measurement of AG-221 concentration. Listing of all sparse PK samples will be provided.

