12.3. Pharmacokinetic Parameters

PK parameters will be determined using non-compartmental (NCA) methods, based on individual plasma concentration-time data for AG-120 from up to 15 subjects with intensive PK assessments on C1D1 and C2D1 in AG-120 treatment arms in Phase 1b.

PK parameters will be determined using non-compartmental (NCA) methods, based on individual plasma concentration-time data for AG-221 from ten to twelve subjects with intensive PK assessments on C2D1 in AG-221 treatment arms in Phase 2. In addition, Listings with sparse PK samples will be provided.

The following PK parameters will be calculated for AG-221 or AG-120 using concentration time data on C2D1 or C1D1/C2D1 from subjects with intensive PK assessments in Phase 2 or Phase 1b:

- AUC_{0-8} : Area under the plasma concentration-time curve from time zero to 8 hours, calculated using the linear trapezoid rule.
- AUC_{0-24} (for AG-221 only): Area under the plasma concentration-time curve from time zero to 24 hours, calculated using the linear trapezoid rule.
- C_{max} : Maximum observed plasma concentration, obtained directly from the observed concentration versus time data.
- T_{max} : Time of maximum observed plasma concentration, obtained directly from the observed concentration versus time data.

[figure not shown]
Additional PK parameters may be determined when appropriate.

All plasma PK parameter calculations will be performed using actual time points. The actual dose of AG-221 or AG-120 will be used for PK parameter calculation. If a dose of AG-221 or AG-120 is missed or is reduced/increased, the complete corresponding concentration-time profile may be excluded from the PK analysis and/or summary statistics after review by Celgene on a case-by-case basis.

PK parameters will be summarized descriptively (mean, standard deviation, CV%, geometric mean, geometric CV%, min, median, and max). Table will be provided.

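### SAP 12.2 should state that the three AG-221 sampling times shared by the intensive and sparse schedules are summarised over all Phase 2 AG-221 subjects; as written, the sparse samples are assigned only a listing

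*SAP*

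**What the plan says.** The protocol's Phase 2 secondary objectives include: "To characterize the PK of oral AG-221 when administered with SC azacitidine". Protocol Table 2 gives the endpoint two parts: "Plasma concentrations and pharmacokinetic parameters of AG-221".

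Protocol Table 7 sets the intensive schedule: C2D1 pre-dose and 2, 3, 4, 6, 8 and 24 hours, then C3D1 pre-dose. Table 8 sets the sparse schedule: C2D1 pre-dose and 4 hours, then C3D1 pre-dose. The Table 8 note says "Sparse pharmacokinetic (PK) sampling for AG-221 will be conducted at all sites during Phase 2", and protocol 6.6 says "The subjects not being assessed for intensive PK in the AG-221 treatment arm during the Phase 2 segments will undergo sparse PK samples".

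SAP 12.2 says that AG-221 and AG-120 plasma concentrations will be summarised descriptively by nominal time. A separate paragraph on the sparse samples then ends: "Listing of all sparse PK samples will be provided". SAP 12.3 limits the non-compartmental parameters to ten to twelve intensive subjects and adds: "In addition, Listings with sparse PK samples will be provided".

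The size of the intensive group is given in several ways:

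- Protocol Table 4, footnote ee: "in Phase 2 for AG-221 subjects at select sites for the first 6 - 12 subjects".
- SAP 17.3, footnote ee: 6 to 12 at select sites.
- Protocol 6.6: the first twelve AG-221 subjects at selected sites.
- SAP 12.2: the first twelve in each Phase 2 treatment arm, although protocol 6.6 takes no PK samples from the azacitidine-alone arm.
- SAP 12.3: ten to twelve.

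**The concern.** Concentrations are half of the stated PK endpoint. If the sparse samples are only listed, the trough and 4-hour summaries describe the first-enrolled subjects at chosen sites. That group is small and is not a random sample of the arm. Samples already scheduled from the rest of the arm would tighten those summaries and show the spread between subjects across all sites. The C3D1 trough, scheduled for everyone, would have no stated summary at all.

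The text also leaves room for two programmers to produce different tables: one pooling everyone with a pre-dose and a 4-hour value, the other using the intensive group alone.

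**Working it through.** The plan states no precision figure for PK, so there is nothing to reproduce. The check is a comparison of schedules, a count, and an illustration of precision.

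**1. Are the sampling times poolable?** The three sparse times are a subset of the intensive times. Protocol 6.6 gives the same C2D1 windows for both groups: within 30 minutes before dosing, and ±10 minutes at 4 hours. Protocol 7.6 has the AG-221 dose given at the site on PK days. Pooling by nominal time is therefore reasonable.

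**2. How many subjects?** SAP 4.4: "A minimum of 99 subjects will be randomized in this phase with 66 subjects in the oral AG-221 + SC azacitidine arm".

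| Intensive group | Share of 66 | Sparse only | Intensive samples (8 each) | Sparse samples (3 each) | Sparse share of samples |
|---|---|---|---|---|---|
| 6 | 9.1% | 60 | 48 | 180 | 180/228 = 79% |
| 10 | 15.2% | 56 | 80 | 168 | 168/248 = 68% |
| 12 | 18.2% | 54 | 96 | 162 | 162/258 = 63% |

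These are scheduled samples, assuming that all are taken. The shared times give 3 × 66 = 198.

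**3. What does pooling gain?** For log-normal concentrations the 95% interval is the geometric mean ×/÷ exp(t × s/√n), where s = √ln(1 + CV²) and t is the 97.5% point on n − 1 degrees of freedom. The documents give no between-subject CV. At an assumed 50%, s = √ln 1.25 = 0.472:

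- n = 10: exp(2.262 × 0.472/3.162) = exp(0.338) = 1.40
- n = 12: exp(2.201 × 0.472/3.464) = exp(0.300) = 1.35
- n = 66: exp(1.997 × 0.472/8.124) = exp(0.116) = 1.12

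On the log scale the n = 66 interval is narrower by a factor of 0.300/0.116 = 2.6 (against 12 subjects) to 0.338/0.116 = 2.9 (against 10).

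Range over assumed CVs:

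| CV | n = 6 | n = 10 | n = 12 | n = 66 |
|---|---|---|---|---|
| 30% | 1.36 | 1.23 | 1.21 | 1.07 |
| 50% | 1.64 | 1.40 | 1.35 | 1.12 |
| 80% | 2.09 | 1.65 | 1.56 | 1.19 |

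The n = 6 column is the footnote minimum and lies below the ten to twelve in SAP 12.3.

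**4. How far does attrition erode this?** n = 66 is a ceiling: it needs every subject to reach C2D1 and C3D1 on drug, at one dose, with usable samples. If only half contributed at one dose (n = 33, for illustration), the factor at CV 50% would be exp(2.037 × 0.472/5.745) = exp(0.167) = 1.18, still tighter than 1.35.

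**The case against.** The strongest reply is that the SAP may already intend pooling. Its nominal-time summary is not expressly limited to intensive samples. SAP 12 applies the PK population to all PK analyses, and SAP 5.2.4 admits anyone with one dose of study drug and one measurable concentration, so sparse subjects qualify. A listing could simply accompany the summary. This reading is possible, and it is why the point concerns what the SAP fails to state. It is still the less natural one. The summary sentence follows the two intensive-sampling paragraphs and leads into a mean concentration plot, and the sparse samples then get their own paragraph with their own output. Even on this reading, C3D1 is absent from the analysis text; it appears only in the SAP 17.3 schedule, which refers back to the protocol tables.

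Three stronger conclusions are tempting, and the documents do not support them:

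- **That the sparse data go unanalysed.** The protocol summary promises to relate 2-HG to AG-221 concentrations over time and does not restrict this to intensive subjects.
- **That no population-PK or exposure analysis exists.** The supplied SAP passes from section 13 to section 17, and an amendment summary lists a protocol section 9.9.3.1, in connection with PK changes, that is not in the supplied text. Absence cannot be inferred.
- **That the whole PK objective rests on 6 to 12 subjects.** Non-compartmental AUC, Cmax and Tmax need the full profile and belong with the intensive group. Only the concentration half of the endpoint could use everyone.

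It is also fair to say that the PK analysis is descriptive, with no precision target, so no stated requirement is failed.

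**Conclusion.** The point holds as a gap in specification with an inexpensive improvement attached. SAP 12.2 and 12.3 assign the sparse samples a listing and do not say whether the nominal-time summary covers them. On the natural reading, the C2D1 pre-dose and 4-hour summaries use about 15% to 18% of the planned AG-221 arm (10 to 12 of 66; 9% at the footnote minimum of 6), and C3D1 has no stated summary.

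At an assumed CV of 50%, pooling would move the interval factor from 1.35–1.40 to 1.12 at best. The size depends on the assumed CV, on log-normality, and on how many subjects reach C2D1 and C3D1 at the same dose. The primary endpoint and the non-compartmental parameters are unaffected.

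**What to change.** In SAP 12.2:

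1. State that C2D1 pre-dose, C2D1 4-hour and C3D1 pre-dose AG-221 concentrations will be summarised over all Phase 2 AG-221 subjects in the PK population with a sample at that time, intensive and sparse pooled, by AG-221 dose being taken. Give n, geometric mean and geometric CV%. A 95% interval and the within-subject C3D1/C2D1 trough ratio are optional.
2. Add C3D1 to the sampling text.
3. Keep the mean concentration-time plot on the intensive subjects, so that two times with many subjects are not joined to others with few. Keep AUC, Cmax and Tmax there too.
4. Give one intensive-subset count, for the AG-221 arm only, and use it in protocol 6.6, both Table of Events footnotes, SAP 12.2 and SAP 12.3.

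The cost is a few lines of text and one descriptive table, with no new samples or visits. The latest amendment rationale says that the primary study report was finalised, so the table may have to be supplementary and labelled as added afterwards.

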12.3. Pharmacokinetic Parameters

PK parameters will be determined using non-compartmental (NCA) methods, based on individual plasma concentration-time data for AG-120 from up to 15 subjects with intensive PK assessments on C1D1 and C2D1 in AG-120 treatment arms in Phase 1b.

PK parameters will be determined using non-compartmental (NCA) methods, based on individual plasma concentration-time data for AG-221 from ten to twelve subjects with intensive PK assessments on C2D1 in AG-221 treatment arms in Phase 2. In addition, Listings with sparse PK samples will be provided.

The following PK parameters will be calculated for AG-221 or AG-120 using concentration time data on C2D1 or C1D1/C2D1 from subjects with intensive PK assessments in Phase 2 or Phase 1b:

- AUC_{0-8} : Area under the plasma concentration-time curve from time zero to 8 hours, calculated using the linear trapezoid rule.
- AUC_{0-24} (for AG-221 only): Area under the plasma concentration-time curve from time zero to 24 hours, calculated using the linear trapezoid rule.
- C_{max} : Maximum observed plasma concentration, obtained directly from the observed concentration versus time data.
- T_{max} : Time of maximum observed plasma concentration, obtained directly from the observed concentration versus time data.

[figure not shown]
Additional PK parameters may be determined when appropriate.

All plasma PK parameter calculations will be performed using actual time points. The actual dose of AG-221 or AG-120 will be used for PK parameter calculation. If a dose of AG-221 or AG-120 is missed or is reduced/increased, the complete corresponding concentration-time profile may be excluded from the PK analysis and/or summary statistics after review by Celgene on a case-by-case basis.

PK parameters will be summarized descriptively (mean, standard deviation, CV%, geometric mean, geometric CV%, min, median, and max). Table will be provided.

13. QUALITY OF LIFE ANALYSIS

[figure not shown]
Two instruments, the European Organization for Research and Treatment of Cancer Quality-of-Life questionnaire (EORTC QLQ-C30) and EuroQoL Group EQ 5D-5L, will be used for evaluating HRQoL outcomes. Description of the analysis is provided in Section 10.2.14.

Data Monitoring Committee (DMC)

An external DMC will be convened. The DMC includes a group of physicians with experience in treating subjects with AML and a statistician, all of whom are not otherwise involved in the study conduct. During the course of the study, the DMC members will periodically review the safety data to ensure the safety of the study subjects. The detailed roles and responsibilities of DMC can be found in the DMC charter.

17. APPENDICES

17.1. Handling of Dates

Dates will be stored as numeric variables in the SAS analysis files and reported in DDMMYYYY format (i.e., the Date9. datetime format in SAS). Dates in the clinical database are classified into the categories of procedure dates, log dates, milestone dates, outcome dates, and special dates.

- **Procedure Dates** are the dates on which given protocol-specified procedure are performed. They include the dates of laboratory testing, physical examinations, etc. They should be present whenever data for a protocol-specified procedure are present and should only be missing when a procedure are marked as NOT DONE in the database. Procedure dates will not be imputed.
- **Log Dates** are dates recorded in eCRF data logs. Specifically, they are the start and end dates for AE and concomitant medications/procedures. They should not be missing unless an event or medication is marked as *ongoing* in the database. Otherwise, incomplete log dates will be imputed according to the rules in [Section 17.2](#) (e.g., for duration or cycle assignment, etc.). However, in listings, log dates will be shown as recorded without imputation.
- **Milestone Dates** are dates of protocol milestones such as randomization, study drug start date, study drug termination date, study closure date, etc. They should not be missing if the milestone occurs for a subject. They will not be imputed.
- **Outcome Dates** are dates corresponding to study endpoints such as survival, progression, etc. In most cases they are derived either from a milestone (e.g., the survival date is derived from the death date), or a procedure date (e.g., the progression date is derived from the date of the hematology lab that was used to determine progression). They may be subject to endpoint-specific censoring rules if the outcome did not occur but are not otherwise subject to imputation.
- **Special Dates** cannot be classified in any of the above categories and they include the date of birth. They may be subject to variable-specific censoring and imputation rules.

Dates recorded in comment fields will not be imputed or reported in any specific format.

17.1.1. Calculation Using Dates

Calculations using dates (e.g., subject's age or relative day after the first dose of study drug) will adhere to the following conventions:

- Study days after the start day of study drug will be calculated as the difference between the date of interest and the first date of dosing of study drug (e.g., lenalidomide) plus 1 day. The generalized calculation algorithm for relative day is the following:
 - If $TARGET\ DATE \geq DSTART$ then $STUDY\ DAY = (TARGET\ DATE - DSTART) + 1$;
 - Else use $STUDY\ DAY = TARGET\ DATE - DSTART$.

Note that Study Day 1 is the first day of treatment of study drug. Negative study days are reflective of observations obtained during the baseline/screening period. Note: Partial dates for the first study drug are not imputed in general. All effort should be made to avoid incomplete study drug start dates. Some analyses may exclude subjects without study drug start date. The SAP may be amended on a case-by-case basis, including guideline and suggestion such as imputing Day 1 by consent date of treated subject.

- Age (expressed in days) is calculated: $AGE = CONSENT - DATE \text{ of BIRTH} + 1$. In practice, age will be transformed to years by dividing the difference by 365.25 days, then truncating.
 - Preference is for using calculated age from clinical database. When not available, calculated age from eCRF or IWRS may be used
 - Partial birth date: impute missing day as 15th of the month; impute missing month as July; set missing age for missing year
- Intervals that are presented in weeks will be transformed from days to weeks by using (without truncation) the following conversion formula:

$$WEEKS = DAYS / 7$$

- Intervals that are presented in months will be transformed from days to months by using (without truncation) the following conversion formula:

$$MONTHS = DAYS / 30.4$$

